#### 1 Protocol version control

Version number	Version Date	Protocol approvals and dates (e.g. REC etc)	Supersedes approved version number/date
V1	17/02/23	Approved: PRE.2023.026	Draft for ethics approval  - amended to V1 following ethics committee suggestions

## 3 Abbreviations

ACR - American college of rheumatology

BSG - Behavioural Sciences Group

COREQ - Consolidated criteria for reporting qualitative research

HCP - Health Care Professional

MCTD - Mixed connective tissue disease

PPI - Patient and Public Involvement

RA - Rheumatoid arthritis

SARD - Systemic Autoimmune Rheumatic Disease

SLE Systemic Lupus Erythematosus

SLICC - Systemic Lupus International Collaborating Clinics

UCTD - Undifferentiated connective tissue disease

# 4 Study Synopsis

Study title	The ADAPT study (Adapting, Disease self-management and							
	Acknowledgement through Psychosocial Targeted interventions)							
Short title	The ADAPT study							
Principal	[name] and [name]							
Investigators								
Chief Investigators'	University of Cambridge							
employing Institution								
Study sponsor	University of Cambridge							
Funder	LUPUS UK and The Lupus Trust							
	·							
Study Duration	3 years (over 2 phases)							
Participants								
Sample size	Phase 1							
	N=120 (n=30 in each of the 3 intervention groups of text messaging							
	intervention, listening support (The Wren Project) and the online physical							
	activity course (Flexifit Pilates) and n=30 in control.							
	Phase 2							
	N=800 (approximately)							
	Numbers dependent on which interventions progress to phase 2, and sample size calculations informed by phase 1. Provisional estimates of N=100 for online physical activity, N=100 for The Wren support, N= 300 for							
	text messaging support and N=300 control.							
	Process and acceptability evaluation interviews with phase 1 participants will take place until theoretical saturation (the point at which no new concepts are generated) is reached. Estimated 15 for each intervention group.							
Objectives	Aim							
	To assess the acceptability, feasibility and effectiveness of methods of remote psychosocial support for SARDs patients. For the interventions trialled (if effective and acceptable) to be incorporated as an adjunct to usual care.							
	Objectives							
	To trial multiple quality of life and mental health measures to determine the most appropriate primary and secondary outcomes for phase 2.							
	To test processes to inform phase 2 effectiveness trial.							
	To develop and trial our own ADAPT instrument to more accurately							

	reflect, measure and monitor SARD patient personal, social and medical satisfaction.  • To assess the acceptability (phase 1) and effectiveness (phase 2) of remote psychosocial interventions on the mental health, wellbeing, self-esteem, resilience, loneliness and disease acceptance of patients with systemic autoimmune rheumatic diseases.
Eligibility criteria	Both phases - Aged 18 years and over  Phase 1: Any INSPIRE (Ethics reference: PRE2022.027) study participant reporting a diagnosis of SLE and requesting on the INSPIRE survey (completed Jul-Sep 23) to be considered for the ADAPT trial.  Phase 2: Reporting a diagnosis of any SARD
Recruitment and group allocation	For both phases, patients expressing an interest in participating in ADAPT at the end of INSPIRE survey will be emailed to confirm continued interest in participating. They will be randomly selected (until trial numbers filled) and then, once consent is given, randomly allocated (block allocation by the study statistician) into one of the intervention or control groups. If INSPIRE study participant responses do not generate sufficient ADAPT participant numbers, additional recruitment will be through online advertising via patient charities and support groups.
Description of intervention	1. Text messages. The text message intervention will be over 8 weeks for each phase and consist of regular (initially twice daily then tapering off gradually as the intervention progresses to 3 x texts a week in the final week) texts. Messages will be a mixture of informative and supportive, and include patient behavioural change techniques. Each automated text will be from named sources (rheumatologist, patient, psychologist and neuropsychiatrist). Participants will be sent the source details at the start, including photos and a link to a recorded video where the sources introduce themselves. The text message intervention will be adapted and improved from patient feedback in the pilot trial. Example texts from the planned programme include:  'Hi [patient name], other people don't always understand how bad the fatigue we get can be. Never feel bad for saying no to doing things when you need to rest!' – [name] (fellow patient)  'Please tell your rheumatologist or GP if you're having any mental health problems. Many people with lupus get them, it's nothing to be embarrassed about and your doctors can only help if you tell them' – [name] (neuropsychiatrist)  The sun can cause a flare in many lupus patients. Please use factor 50 sunscreen, cover up and avoid the sun as much as possible [name] (rheumatologist)  Hello [name], remembering to take lots of medications can be hard for anyone. If you're struggling, try using a Dossett box, setting alarms or have the tablets next to where you get breakfast so it becomes a routine' [name] (psychologist).

Some text messages will also contain links to support or educational sources, or to short videos from each source giving additional advice and support.

Text topics have been informed by the INSPIRE study results on the impact of the disease on patient lives and the most common (and/or most distressing) neuropsychiatric symptoms experienced in this patient group, and from the study team's respective experiences.

Text intervention group participants (if willing) will also be joined into WhatsApp groups with 3-5 other text intervention participants with guidance provided on providing mutual understanding and support. A researcher will set up each group, provide introductions and initial suggestions for discussion and then leave the group. Groups will also be requested to discuss the intervention and their opinions, and make suggestions for improvements at follow-ups.

This will help reduce participants feeling abandoned at the end of the intervention as they may continue with the WhatsApp groups for as long as they wish (outside of the study).

#### 2. Listening support.

This will be provided by The Wren Project, in line with their standard programme of offering listening support (via Zoom) by a trained 'listener' (as opposed to counsellor) to patients with an autoimmune disease. Each Ppt will have fortnightly 50 minute one to one 'talking' sessions over 12 weeks. The focus will be talking about the impact of the disease and coping.

#### 3. Physical activity course

This will be provided by a trained Pilates instructor (Flexifit Pilates) via Zoom. Participants will receive the intervention in groups of 15, twice a week, in 50-minute sessions over 8 weeks via Zoom. Exercises will be tailored to Ppts with chronic diseases with the emphasis on participation, social interaction and enjoyment.

#### 4. Post-study support

Follow-up support will also be available to The Wren intervention Ppts in line with The Wren projects usual follow-up procedures. This consists of joining a group of 'graduate Wrens' with regular contact (if desired) with the organisation and each other. Similarly, Ppts in the physical activity intervention will be offered attendance (at small cost) in weekly sessions outside of the study for people with chronic conditions. This will be following their courses (intervention period) finishing.

#### Data collection

Baseline survey: On entry into the ADAPT trial prior to being randomised to an intervention or the control group.

Follow-up 1: Baseline + 12 weeks.

Follow-up 2: Baseline + 6 months to more accurately ascertain potential longer-term effects.

In-depth interviews will be carried out with purposively selected participants from questionnaire responses. Interviews will also be carried out during the interventions (in phase 1 only) to assess views of different intervention components, in order to refine the interventions and processes for phase 2.

Analysis	Qualitative - Thematic analysis including using Nvivo 12 software								
	Quantitative – Descriptive and inferential statistics, including multiple regression analysis.								

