#### 6.4 Consent

The process for obtaining participant informed consent will be in accordance with ethical guidelines and Good Clinical Practice. Potential participants from the INSPIRE study will be asked whether they wish to consider taking part, emphasising that participation is entirely voluntary. The participant information sheet, questionnaire and consent form will be sent by email to interested INSPIRE study Ppts, and made available online if INSPIRE Ppts do not generate sufficient numbers. There will be an opportunity to ask questions. Consent for both phases of the psychosocial trials (including to potentially be interviewed) will be requested electronically at the start of the baseline questionnaires. Consent for the interview and to be audio-recorded will also be verbally taken at the start of the interview with the consent statements audio recorded.

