#### Follow-ups

Follow-up 1 - Baseline+ 12 weeks

Follow-up 2 - Baseline + 6 months

Participants will be sent up to 3 email reminders for non-response to the follow-up questionnaires.

#### 6.7 Selection of outcome measures for phase 2

Phase 2 primary and secondary outcome measures will be selected from the analysis of phase 1 quantitative and qualitative results. Following phase 1 analysis, the multidisciplinary ADAPT study team will meet to decide which intervention(s) will proceed to phase 2 and which outcome measures to select for phase 2. The selection criteria will include (with most weight given to patient views on importance):

- 1. Acceptability and perceived importance and relevance of each measure to patients. These will be assessed quantitively by questions on the survey about each instrument, and qualitatively during interviews. Any measures that are rated as unacceptable or irrelevant by >25% of participants will be excluded. Participants will be asked to rank the measures in terms of importance to them and a mean score calculated. The top 3 scoring outcome measures will be discussed, taking into account additional patient views from interviews, team views and sensitivity as detailed below to select one measure for the primary outcome measure. Other measures will be considered for inclusion as secondary outcomes, by considering the ordering of patient scores, and patient willingness to complete different lengths of follow-up surveys. A minimum of one phase 1 outcome measure will be excluded for phase 2.
- 2. Sensitivity of each measure to change by psychosocial interventions. Short-term effectiveness of each intervention will be measured by using the within-person change from baseline to follow-up one, for each phase 1 instrument.

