#### 7.9 Proposed study timetable and proposed outputs

	2023			2024				2025
	Jan 2023	April 23	May- Dec 23	Jan- Mar 24	Apr- Jul 24	Aug- Oct 24	Nov - Dec 24	2025
Produce draft protocol	Х							
Finalise participant information sheets and surveys	x							
Submit ethics proposal	Χ							
Trial surveys	Х							
INSPIRE Ppts who expressed interest in ADAPT contacted and randomised if consenting to participate		х						
Interventions commence.  Text messages and controls: All commence in /May 23  The Wren project: 5 ppts commence intervention per month  Online exercise: First group of 15 ppts commences in Apr, second group in Sep 23			х					
Interviews with selected participants		х	Х	х				

Follow-ups at individual ppts F-up 1 and 2 points		Х					
Final follow-up 2s for later intervention ppts (initially controls)			х				
Initial analysis and assessment of adaptions to interventions required for phase 2, and development of stage 2 interventions			х	х			
Phase 2 commences					х		
Phase 2 follow-ups						Х	Х
Quantitative and overall analysis (separate analysis for each phase and combined final analysis) and draft papers				х	х	х	х
Qualitative analysis (ongoing throughout interventions and post-intervention in-depth interviews	х	х	х	х	х	х	х
Publications					Х		Х

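### Both follow-ups are timed from a pre-randomisation baseline, but the timetable staggers Wren and Pilates starts, so follow-up 1 precedes the course for half the Pilates arm and about a third to two-thirds of the Wren arm

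*Protocol*

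**What the plan says.** **Time zero.** The synopsis (section 4, Data collection) fixes the baseline: "Baseline survey: On entry into the ADAPT trial prior to being randomised to an intervention or the control group". Section 6.4 agrees, since consent "will be requested electronically at the start of the baseline questionnaires". Both follow-ups run from that point in the synopsis and again in section 6.6: "Follow-up 1 - Baseline+ 12 weeks", with follow-up 2 at six months.

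**Arms.** The synopsis gives "N=120 (n=30 in each of the 3 intervention groups of text messaging", listening support and online physical activity, and "n=30 in control".

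**Calendar.** Section 7.9 marks contact and randomisation in a single column, April 2023. It then gives three start patterns:
- Text and control: everyone in May 2023.
- Wren: "The Wren project: 5 ppts commence intervention per month".
- Pilates: "Online exercise: First group of 15 ppts commences in Apr, second group in Sep 23".

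A further row reads "Final follow-up 2s for later intervention ppts (initially controls" (closing bracket omitted).

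**Use of follow-up 1.** Section 6.7 (selection of outcome measures) makes each participant's change between baseline and follow-up 1 the measure of short-term effectiveness and of how sensitive each instrument is to change. Section 6.3 says phase 2 will be sized from phase 1 indications of effectiveness.

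**The concern.** The questionnaire clock and the delivery clock are set independently. A clock that starts before randomisation works when every arm starts soon afterwards. Here two of the three interventions have intakes spread over about five months, while the first follow-up comes at 12 weeks. People allocated to a late intake would answer follow-up 1 without having met the intervention.

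This would weaken the apparent change for Wren and Pilates but much less for text. The three interventions would then not be compared on equal terms, and instruments could look insensitive because the course had not been given. Follow-up 2 is meant to show longer-term effects, but would fall during the course for late starters. Data not collected at the right time cannot be recovered in the analysis.

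The row on participants who are initially controls adds a second problem. It suggests that some late starters serve as controls first, or that controls later receive an intervention. Neither fits a separate randomised control arm of 30.

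**Working it through.** **Inputs from the protocol.** 30 per arm (section 4); Wren course 12 weeks, or 84 days; Pilates course 8 weeks, or 56 days, in classes of 15; text course 8 weeks; start dates as in section 7.9.

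**Stated figures reproduced.** 3 × 30 + 30 = 120. Pilates: 2 × 15 = 30. Wren: 30 / 5 = 6 monthly intakes.

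**Assumptions.** Baseline on 15 April 2023, and Wren intakes on the 1st of each month from May to October. Follow-up 1 is then 8 July and follow-up 2 is 15 October. Share delivered = days from start to follow-up / course length, limited to 0–100%.

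| Wren intake (5 people each) | Weeks after baseline | At follow-up 1 | At follow-up 2 |
|---|---|---|---|
| 1 May | 2.3 | 68/84 = 81% | 100% |
| 1 June | 6.7 | 37/84 = 44% | 100% |
| 1 July | 11.0 | 7/84 = 8% | 100% |
| 1 August | 15.4 | 0 | 75/84 = 89% |
| 1 September | 19.9 | 0 | 44/84 = 52% |
| 1 October | 24.1 | 0 | 14/84 = 17% |
| Mean | | 112/504 = 22% | 385/504 = 76% |

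In this case 15 of 30 Wren participants have not started at follow-up 1, and none has finished.

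**Sensitivity for Wren at follow-up 1.** The first intake month is not stated, so April and May were both tried, with intakes on the 1st, 15th or 28th.

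| Baseline | First intake | Not started (of 30) | Mean delivered |
|---|---|---|---|
| 15 April | April | 10–15 | 24–39% |
| 15 April | May | 15–20 | 10–22% |
| 1 to 28 April | April | 10–20 | 17–47% |
| 1 to 28 April | May | 15–25 | 5–30% |

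**Pilates.** With a mid-April baseline the first class has finished by follow-up 1. The second 15 have had nothing, and this holds for any April baseline, because follow-up 1 is then no later than 23 July. At follow-up 2 (15 October) the second class has had 44/56 = 79% if it starts on 1 September and 15/56 = 27% if it starts on 30 September. Over baselines from 1 to 28 April the range is 2–100%.

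**Text.** By 8 July a 15 May start has delivered 54/56 = 96% and a 31 May start 38/56 = 68%. Everyone has started.

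**Totals at follow-up 1 (mid-April baseline).** Not started: 15 Pilates plus 10–20 Wren = 25–35 of the 60 in those arms. In the tabulated case it is 30 of 60, or 30 of all 90 intervention participants.

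**The other reading, counting from course start.** Every Wren and Pilates course is then over by start + 12 weeks. But the second Pilates class starts about 20–24 weeks after a mid-April baseline, so its baseline-to-follow-up-1 interval is 20 + 12 = 32 to 24 + 12 = 36 weeks. It is 12 weeks for controls measured from baseline. The last follow-up 2 would fall in March 2024 (Wren from April; Pilates) or April 2024 (Wren from May). That could explain a separate row for late follow-up 2s, but the protocol nowhere defines this time zero.

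**The case against.** **The dates are inferred.** No rule says that all 120 baselines fall in April; this comes from one cell of a proposed timetable. The calendar is unreliable elsewhere: section 6.2 dates the INSPIRE survey to July–September 2023, after the supposed randomisation. The table is damaged in extraction, so the exact column of the row on late follow-up 2s is uncertain. The first Wren intake month is not given. All of this stands, and it is why the Wren result is a range.

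**Staggered entry could remove the problem.** If people were enrolled just before their course, baseline and start would coincide. But the arm is unknown at baseline and allocation is in blocks across all arms. Staggered entry would therefore stagger text and control too, and section 7.9 starts all of those in May. The timetable also has a row for follow-ups at each person's own points, but the protocol defines those points only from baseline.

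**Phase 1 is about acceptability.** Effectiveness is a phase 2 objective. Outcome selection gives most weight to patients' views, the progression thresholds are not tied to follow-up 1, and interviews also collect acceptability. This limits the damage. It does not remove it, because section 6.7 still gives the change to follow-up 1 a defined role.

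**Stronger readings to avoid.** A reader might infer that follow-up 1 measures mostly untreated people. The figures do not show that: Pilates is exactly half, the first class has finished, all text participants have started, and about a third of all intervention participants are unstarted in the tabulated case. A reader might also turn the delivery shares into a multiple by which phase 2 would be oversized. That needs benefit strictly proportional to course received, which the protocol does not support, and section 6.3 names no follow-up as the source of the phase 2 calculation. Nor is it established that controls cross over; one row suggests it.

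A baseline before randomisation is correct practice. The fault lies in the gap between it and the start of treatment.

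**Conclusion.** The point holds as an unreconciled conflict between the follow-up definitions (sections 4 and 6.6) and the timetable (section 7.9), with consequences for what phase 1 can show. Followed as written with April baselines, 15 of 30 Pilates participants and about 10 to 20 of 30 Wren participants have had no intervention at follow-up 1. The Pilates figure does not depend on the day in April. The Wren figure depends on the month and day of the first intake and reaches 25 at the extreme.

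The change to follow-up 1 is therefore diluted for Wren and Pilates, and much less for text. How far it is diluted depends on how benefit builds up over a course, which the protocol does not say. The same change is likely, though not stated, to inform the size of phase 2.

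Counting from course start instead does not rescue the plan as written: that time zero is undefined, the baseline is months old for late starters, and controls have no matching survey times. The row on participants who are initially controls conflicts with a separate control arm on either reading.

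**What to change.** **Preferred.** Keep the baseline before randomisation. Obtain consent, take baseline and randomise in batches timed to the Wren and Pilates intakes, with all four arms in each batch and the text and control clocks starting with their batch. Take each baseline immediately before the batch starts: the Wren course itself lasts 12 weeks, so any gap puts follow-up 1 before its end. Follow-up 1 then falls at or after course end, and all arms share the same calendar windows.

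**If randomisation must stay in one April wave.** Keep that baseline for the randomised comparison. Time follow-ups 1 and 2 for late starters from their course start, and survey a pre-specified random subset of controls at the same times. Any repeat questionnaire before a late start should be supplementary only, because it is answered after allocation is known.

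**In either case.** State time zero for each arm in sections 4 and 6.6 and make section 7.9 agree. Reconcile the row on participants who are initially controls with section 4: no person contributes to two arms, and control data count only while the control is untreated.

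**Cost.** Under the first option text starts are staggered. Batches must also reconcile Wren's five a month with Pilates classes of 15: 15 Wren places take 15 / 5 = 3 monthly intakes, so batch sizes need agreeing with both providers. Under the second option some control surveys move, and each late comparison rests on fewer than 30 controls. Under either, the last follow-up 2 moves to about March–April 2024.

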## 5 Study background and rationale

Systemic autoimmune rheumatic diseases (SARDs) have significant and lifelong negative impacts on patients' physical and mental health, and quality of life. SLE in particular has been found to increase the risk of mental health symptoms (1, 2) which have a major impact on QoL(3). The prevalence of depression in SLE is estimated at 30–50% (1, 2), and one study found that 20–50% of rheumatology patients have psychosocial problems attributable to their disease, which were frequently not discussed with their physician (4). MH problems, ongoing trauma and post-traumatic stress disorder (PTSD) in response to misdiagnoses and/or the impact of chronic illness have been reported in other studies (5, 6).

Although approximately 50% of rheumatology patients in our earlier studies (7, 8) reported either good or excellent support for their disease overall and from their rheumatologist, there were common gaps in care identified. There was a clearly expressed need for more support for patients in coming to terms with a life-changing chronic disease and more consideration of psychosocial needs and quality of life. In addition, a recent study found that the majority of respondents with rheumatic diseases struggled to cope with their condition, yet only 16% had been offered psychological support from the UK National Health Service (9). Time constraints in clinic mean that discussion of MH, QoL and coping/ adaptation strategies can often not be a priority for physicians who are understandably focused on preventing organ damage, and patients are thus required to seek support elsewhere. Rheumatology clinicians in our exploratory work stated they felt psychosocial support and MH was an unmet need that they could not feasibly address within the NHS time constraints.

With the ongoing impact of changes to care from Covid-19 having reduced the frequency of rheumatology appointments for many patients, large back-logs and less contact with clinicians, there has been a widespread sense of abandonment expressed by this patient group (10). There is thus an even greater urgency to ensure (and provide evidence for NHS funding) adequate psychosocial support and patient-education through other means especially as these can be the first casualty of increased physician time constraints (11). Many of this patient group were in the clinically extremely vulnerable classification for Covid-19 risk (12). With Covid-19 becoming endemic, a degree of risk is highly likely to continue long into the future and many of these patients remain very cautious about face-to-face contact. Trialling remote interventions is therefore of key importance and will ensure those who are most fearful and/or vulnerable from infection will not be excluded. In addition to infection risks of face-face interventions, remote interventions may also be preferable to some of the lupus population where high levels of debilitating fatigue are prevalent.

Chang et al carried out a recent systematic review of remote and in-person psychosocial interventions in SLE patients (13). This included a range of interventions, such as different exercise-based activities (14, 15), and counselling (16), of which many demonstrated significant improvements in outcome measures. Outcome measures in previous SARD psychosocial studies have been largely QoL measures, such as SF36, depression and/or anxiety, and disease activity measures. A minority of studies have focused on psychological distress (17) or coping strategies (18). Our current INSPIRE study (unpublished) results suggests that loneliness has a major negative impact on SARD patient QoL. Although this has been explored in other conditions, and Mann et al reported an association between loneliness and onset of depression (19), as far as we know it has not been studied in SLE. Resilience is an important aspect of adapting to living with chronic diseases, yet few studies (20) have assessed resilience in SLE, or the wider SARD population. Therefore, we will be trialling measures of loneliness and resilience in addition to the more commonly assessed QoL, depression and anxiety.

The three interventions to be trialled are:1) An online exercise course, 2) The Wren Project listening support, and 3) a text messaging support programme. The interventions have been selected based

on patient surveys eliciting their priorities for methods of support, and to attempt to fill some of the multiple gaps in the literature identified.

